### PROCEDURE CODE:

Procedure	Kubun code	Description
Hemodialysis	C102	Home self-peritoneal irrigation guidance management fee
	C102-2	Home hemodialysis frequent time guidance management
	C155	Automated peritoneal irrigation equipment add-on fee
	J038-2	Continuous mild blood filtration
	J038-21	Impaired people add-on fee (continuous mild hemofiltration)
	J038-22	Impaired people add-on fee (continuous mild hemofiltration)
	K635-3	Catheter intraabdominal placement for continuous ambulatory peritoneal dialysis
Joint replacement	K082-21	Artificial joint removal (knee)
	K082-22	Artificial joint removal (foot)
	K082-23	Artificial joint removal (finger)
	K082-31	Artificial joint reimplantation add-on fee (knee)
	K082-32	Artificial joint reimplantation add-on fee (foot)
	K082-33	Artificial joint reimplantation add-on fee (finger)
	K082-4	Total joint replacement of autologous costal bone and cartilage
	K082-5	Total artificial talus replacement
	K082-6	Hip prosthesis sliding surface exchange
	K083	Direct traction using steel codes, and others
Pregnancy	K083-2	Arthrodesis for clubfoot using foot plate and pinch bar
	K890	Tuboplasty (tubo-ovarian transplant, tubal bypass procedure and others)

Proprietary confidential information © 2022 Boehringer Ingelheim International GmbH or one or more of its affiliated companies

	K890-2	Falloposcopic tuboplasty
	K890-3	Laparoscopic salpingoplasty
	K891	Hysterocervicotomy during delivery (including suture)
	K892	Vaginal breech delivery
	K893	Aspiration delivery
	K8941	Outlet/low forceps delivery
	K8942	Middle forceps delivery
	K895	Perineal/vulvar incision and suturing (during delivery)
	K8961	Perineal/vaginal tear suturing (during delivery) (with involvement of the muscular layer)
	K8962	Perineal/vaginal tear suturing (during delivery) (with involvement of the anal)
	K8963	Perineal/vaginal tear suturing (during delivery) (up to vaginal fornix)
	K8964	Suturing of perineal/vaginal tear (associated with rectal tear) (during delivery)
	K897	Endocervical tear suturing (during delivery)
	K8981	Caesarean delivery (emergency cesarean section)
	K8982	Cesarean section (selective cesarean section)
	K8983	Complication add-on fee (hysterotomy)

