#### **Exclusion Criteria**

1. Diagnosed with end-stage renal disease (ESRD), or undergo hemodialysis, or experience pregnancy during the study period
2. Initiate warfarin, dabigatran, rivaroxaban due to valvular AF (VAF), AF associated with mechanical valve malfunction or mechanical complication of heart valve prosthesis, or rheumatic AF
3. Underwent joint replacement procedures or diagnosed with venous thromboembolism during the look-back period prior to or on the index date
4. Prescribed with more than 1 OAC on the index date

---

Proprietary confidential information © 2022 Boehringer Ingelheim International GmbH or one or more of its affiliated companies

5. Prescribed with more than 2 anti-platelet drugs per prescription (triple or quadruple anti-platelet use), or prescribed with any anti-platelet injection
6. Patients with missing or ambiguous age or sex information

The codes for OAC are listed in [Annex 1](#) and codes to select study population (in/exclusion criteria) are listed in [Annex 2](#).

NVAF during the look-back period prior to or on the index date is defined as patients had diagnosis of AF and had no diagnosis of VAF during the specific period.

Pregnancy during the study period is defined as patients had any of the following:

- Confirmed diagnosis of pregnancy in the study period.
- In FF1 data (discharge summary data), the admission date was within the study period, and returned true for the pregnancy flag or the number of weeks of pregnancy at the time of hospitalization greater than 0 or the number of weeks of pregnancy at the time of delivery greater than 0.
- Medical treatment of pregnancy in the study period.

AF associated with mechanical valve malfunction or mechanical complication of heart valve prosthesis is defined as a record with diagnosis of AF and diagnosis of mechanical valve malfunction or mechanical complication of heart valve prosthesis.

Rheumatic AF is defined as a record with diagnosis of AF and diagnosis of rheumatic heart disease.

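### The SAP's hemodialysis procedure list has no code for haemodialysis given at a facility, so such patients are excluded only if a listed ESRD or dialysis diagnosis is also recorded

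*SAP*

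**What the plan says.** SAP section 7.3, exclusion criterion 1, reads: "Diagnosed with end-stage renal disease (ESRD), or undergo hemodialysis, or experience pregnancy during the study period". The three conditions are joined by *or*, so any one is enough. Protocol section 9.2.2 has the same criterion.

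The same SAP section makes the criteria operational by stating that "codes to select study population (in/exclusion criteria) are listed in" Annex 2. For this criterion Annex 2 has an ESRD block in the diagnosis table and a Hemodialysis block in the procedure table. The only entry in the Hemodialysis block whose description names hemodialysis is C102-2, "Home hemodialysis frequent time guidance management". The Hemodialysis block is printed in full. It is not deferred to an attached file, as the pregnancy diagnoses and the oral antiplatelet drugs are.

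SAP section 10.2 adds that when no code for a condition is found, the condition is taken to be absent.

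**The concern.** The plan names hemodialysis as a ground for exclusion separate from an ESRD diagnosis, so the procedure codes should be able to find hemodialysis on their own. The listed codes cover treatment at home, peritoneal treatment and continuous filtration, but not haemodialysis delivered at a facility. The data come from acute care hospitals (Protocol section 9.4), where facility treatment is what procedure records would be expected to show.

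The comparability of the arms on the primary outcome is at stake. Suppose dialysis patients bleed more and are unevenly divided between warfarin and the NOACs. Any who remain would then distort the major-bleeding hazard ratio unless the weighting model can identify them. If they were concentrated in the warfarin arm, the distortion would make the NOAC look safer.

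**Working it through.** No sample size, event count or power figure enters this point. The check compares the code lists with the criterion.

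**Step 1. The procedure limb (SAP Annex 2, procedure codes, Hemodialysis).**

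| Code | SAP description | Type |
|---|---|---|
| C102 | "Home self-peritoneal irrigation guidance management fee" | peritoneal |
| C102-2 | "Home hemodialysis frequent time guidance management" | home haemodialysis |
| C155 | "Automated peritoneal irrigation equipment add-on fee" | peritoneal |
| J038-2 | "Continuous mild blood filtration" | continuous filtration |
| J038-21 and J038-22 | "Impaired people add-on fee (continuous mild hemofiltration" (both rows) | add-on fees for continuous filtration |
| K635-3 | "Catheter intraabdominal placement for continuous ambulatory peritoneal dialysis" | peritoneal |

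Count by description: 3 peritoneal + 1 home haemodialysis + 3 continuous filtration + 0 facility haemodialysis = 7.

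**Step 2. The diagnosis limb (SAP Annex 2, diagnosis codes, ESRD).** The list runs from N16.5 to Z99.2. It includes N18.5 (chronic kidney disease stage 5), Z49 with Z49.0 to Z49.2 (dialysis care, with Z49.1 being extracorporeal dialysis), Z99.2 (dialysis dependence), T82.4 and Y84.1. Z49.1 is not restricted by place of treatment. N18.5 is the only N18 code listed. In the extracted text the row labels of this table are displaced. The descriptions, and the repeat of T82.4 in the later T82 block, show which rows belong to ESRD.

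**Step 3. The two limbs together.**

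| Patient | Procedure limb | Diagnosis limb | Result |
|---|---|---|---|
| Home haemodialysis, peritoneal dialysis or continuous filtration, with a listed procedure code | met | not needed | excluded |
| Facility haemodialysis with a listed ESRD or dialysis diagnosis | not met | met | excluded |
| Facility haemodialysis, no listed diagnosis | not met | not met | stays in |

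The third row is the gap. Examples are a patient dialysed under another renal diagnosis with no dialysis diagnosis recorded, or temporary dialysis without ESRD. Under SAP section 10.2 the criterion treats such a patient as not on dialysis.

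**Step 4. What adjustment can do.** SAP section 11.1 puts all Annex 4 covariates except two antiplatelet variables into the propensity model. Two of these carry renal information. Renal dysfunction is yes/no. The HAS-BLED score (SAP section 8.3) gives a single point for any of renal dysfunction, hemodialysis treatment, hepatic dysfunction, cirrhosis, renal transplant, raised creatinine, raised liver enzymes or raised bilirubin. Neither variable separates dialysis from milder disease.

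**Step 5. Size.** The documents give neither the frequency of facility haemodialysis nor the share of those patients without a listed diagnosis. The number retained cannot be computed.

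**The case against.** The strongest reply is that the criterion is one *or* rule and its diagnosis limb is broad. A facility patient with any listed code at any time in the study period (April 2011 to December 2020, SAP section 7.2) is excluded. That stands. A reader might infer from the procedure list that the exclusion fails to remove haemodialysis patients in general. The documents do not support this: only patients without a listed diagnosis get through, and home haemodialysis has its own code.

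A reader might also infer that yes/no renal dysfunction is the only renal covariate in the weighting. It is not, because HAS-BLED enters too. The codes behind its hemodialysis item are in an attached file that is not shown, so they may differ from Annex 2. What remains true is that a one-point composite does not isolate dialysis.

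A third tempting step is to put a figure on the bias. With a fraction c of the warfarin arm retained, none in the NOAC arm, and a bleeding rate RR times higher, the hazard ratio is multiplied by 1/((1 − c) + c × RR). Assuming c = 0.01 and RR = 2 gives 1/1.01 = 0.99; assuming c = 0.05 and RR = 3 gives 1/1.10 = 0.91. None of these inputs, nor the one-sided split, is in the documents. Five per cent of the roughly 17000 warfarin patients (Protocol section 9.5) would be 850 people on dialysis with no listed code in the whole study period. The calculation also ignores the weighting. It is no estimate of the bias.

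Finally, the code descriptions appear to be translated and no code dictionary is supplied, so the reading rests on the printed descriptions. Some row labels in the procedure table are displaced too, but the seven descriptions run unbroken and nothing suggests a lost row.

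**Conclusion.** The point holds in a limited form. As printed, the hemodialysis limb of exclusion 1 does not capture facility haemodialysis. For those patients the exclusion depends entirely on a listed ESRD or dialysis diagnosis. Patients with facility dialysis on procedure records alone remain in the cohort, and the covariates do not distinguish them from patients with milder renal disease.

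Their number and their spread across the arms are unknown, so neither the size nor the direction of any bias can be stated. If nearly all facility patients carry a listed diagnosis, the effect is negligible. The SAP does not say that they do, nor why diagnosis codes would suffice. The conclusion assumes that the printed list is the one that will be run and that its descriptions are accurate.

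Whether the criterion should run over the whole study period is a separate question. This point does not depend on it.

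**What to change.** Add the procedure codes for haemodialysis and haemodiafiltration given at a facility to the Hemodialysis list in SAP Annex 2. If the sponsor prefers to leave the list as it is, the SAP should state why the diagnosis codes are enough.

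In either case, tabulate by treatment group how many patients are excluded by procedure only, by diagnosis only and by both, with the facility codes included in the count. The patient flow shell (SAP Annex 5, Table 1) puts ESRD, hemodialysis and pregnancy in one row, so it would not show this. The procedure-only count from the added codes is the number that the present list would have left in, and it settles the unknown size.

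The cost is a code-list edit, a few table rows and the loss of what is probably a small number of patients. One limit remains: the database is not a closed healthcare system (Protocol section 9.9), so dialysis given outside the participating hospitals will still be visible only through diagnoses.

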# BOEHRINGER INGELHEIM Group of Companies

## Statistical and Epidemiological Analysis Plan (SEAP) for Non-Interventional Studies (NIS)

c38948754-01

Page 20 of 32

Proprietary confidential information © 2022 Boehringer Ingelheim International GmbH or one or more of its affiliated companies

	T82.9	Unspecified complication of cardiac and vascular prosthetic device, implant and graft
Rheumatic heart disease	I09	Other rheumatic heart diseases
	I09.0	Rheumatic myocarditis
	I09.1	Rheumatic diseases of endocardium, valve unspecified
	I09.2	Chronic rheumatic pericarditis
	I09.8	Other specified rheumatic heart diseases
	I09.9	Rheumatic heart disease, unspecified
Venous thromboembolism	I26	Pulmonary embolism
	I26.0	Pulmonary embolism with mention of acute cor pulmonale
	I26.9	Pulmonary embolism without mention of acute cor pulmonale
	I80.2	Phlebitis and thrombophlebitis of other deep vessels of lower extremities
Pregnancy	codes presented in the following excel file:   1160-0308 diagnosis_pregnancy.xls	

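### The Annex 2 joint-replacement codes do not fully or accurately implement exclusion 3: no row describes a first hip, knee or shoulder replacement, and two rows are not joint replacement

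*SAP*

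**What the plan says.** Protocol 9.2.2 and SAP 7.3 give exclusion 3 in the same words: "Underwent joint replacement procedures or diagnosed with venous thromboembolism during the look-back period prior to or on the index date". SAP 7.3 adds that "codes to select study population (in/exclusion criteria) are listed in" Annex 2.

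In Annex 2 the procedure table has a block labelled joint replacement, with codes from K082-21 to K083-2. One row is "Total joint replacement of autologous costal bone and cartilage". The last two rows in code order are "Direct traction using steel codes, and others" (K083) and "Arthrodesis for clubfoot using foot plate and pinch bar" (K083-2).

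The VTE block in the diagnosis table has four rows: I26, I26.0 and I26.9 for pulmonary embolism, and I80.2, "Phlebitis and thrombophlebitis of other deep vessels of lower extremities".

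For pregnancy diagnoses and anti-platelet drugs, Annex 2 refers to separate Excel files. For joint replacement and VTE it refers to none, so the printed rows are the working definition.

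**The concern.** The criterion speaks of joint replacement in general. A reader would expect its code list to include the first implantation of an artificial hip, knee or shoulder. The printed list has no such row, yet it contains a traction code and a clubfoot operation. Applied literally, it errs both ways: it keeps patients the criterion excludes and removes patients it does not mention.

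Three features of the plan raise the stakes.

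- **Indication.** The inclusion criteria require one AF diagnosis and one CAD diagnosis. They do not require that the anticoagulant was started for AF. Neither document states a purpose for exclusion 3, but removing patients with a competing reason for anticoagulation is the natural reading, and no other criterion screens for recent joint surgery.
- **Adjustment.** Annex 4 lists neither joint replacement nor VTE as a covariate, so the propensity model does not balance them directly.
- **Outcome.** The Annex 3 outcome codes include acute anaemia after haemorrhage (D62), and SAP 8.2.1 counts transfusion in either setting. Recent major surgery could therefore touch the primary outcome.

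There is also a reporting issue. Table 1 in SAP Annex 5 has a row for patients removed under exclusion 3. Readers would take that count to cover joint replacement generally.

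**Working it through.** The plan states no figure on this point, so the check compares the wording of the criterion with the printed rows.

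**Joint-replacement block, SAP Annex 2, in code order**

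| Codes | Rows | Content | Class |
|---|---|---|---|
| K082-21, -22, -23 | 3 | Removal of a prosthesis: knee, foot, finger | Removal |
| K082-31, -32, -33 | 3 | Add-on fee for reimplantation: knee, foot, finger | Replacement or revision |
| K082-4 | 1 | Joint replacement with costal bone and cartilage | Replacement or revision |
| K082-5 | 1 | Artificial talus | Replacement or revision |
| K082-6 | 1 | Exchange of the sliding surface of a hip prosthesis | Replacement or revision |
| K083 | 1 | Direct traction | Not joint replacement |
| K083-2 | 1 | Clubfoot arthrodesis | Not joint replacement |

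Total: 3 + 3 + 1 + 1 + 1 + 1 + 1 = 11 rows.

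- Replacement or revision: 3 + 1 + 1 + 1 = 6.
- Removal: 3.
- Not joint replacement: 2.
- First hip, knee or shoulder replacement: 0. The knee appears only under removal and reimplantation, the hip only under exchange of part of an existing prosthesis, and the shoulder not at all.

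**Is a row missing?** Every K082 entry is a sub-code and K082 itself is not printed, whereas C102, K083 and K890 are printed alongside their sub-codes. This hints at an omission and no more: J038-2 is also printed without J038, and the documents do not say what K082 covers or whether codes are matched by prefix.

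**Does K083-2 belong to this block?** In the machine-read text the pregnancy label falls beside this row. Labels are shifted elsewhere in Annex 2 as well: the ESRD label falls beside I25.0, an atherosclerotic heart disease code. The shift is an artefact of reading the table, and by code order K083-2 follows K083. If the row is set aside, traction remains and the first replacements are still absent.

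**VTE block.** Four rows: three for pulmonary embolism and one for deep leg veins. The word *other* in the I80.2 description implies that some deep leg vessels are coded elsewhere. The documents do not show which codes those are or how often they are used.

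**The case against.** **What stands against the point.** The criterion names no particular joint and does not separate first from revision surgery, so it would be wrong to say that it names primary hip, knee or shoulder replacement. Six of the 11 rows do concern replacement or revision. Every patient must also have AF and CAD diagnoses and no oral anticoagulant in the look-back period, so a recent joint operation does not show that the drug was started for another reason. Follow-up stops at discontinuation, which limits the person-time of short-course users. All of this lowers the likely impact. None of it makes a list without first hip, knee or shoulder replacements match a criterion that covers joint replacement generally.

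**Stronger readings that the documents do not support.**

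- *Exclusion 3 is not implemented, and nearly all the patients it targets stay.* Pulmonary embolism, one deep-vein code and six replacement or revision rows are covered. No frequencies are given, so the share kept is unknown.
- *The VTE list is deficient.* The wording of I80.2 justifies a check. Saying which diagnoses are missed would need the full classification, which the documents do not give.
- *The hazard ratio moves by 1-3%.* Suppose a share p of one arm is wrongly kept and has twice the event rate. That arm's rate is multiplied by (1 − p) + 2p = 1 + p. For p from 0.01 to 0.03 the hazard ratio is multiplied by 1.01 to 1.03 if the arm is the NOAC, or by 1/1.01 = 0.99 to 1/1.03 = 0.97 if it is warfarin. With the same p and the same doubling in both arms the factor is (1 + p)/(1 + p) = 1. Both p and the doubled rate are assumptions, so this illustrates the mechanism and does not estimate the bias.

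**Conclusion.** The point holds for the joint-replacement half of exclusion 3. The list that SAP 7.3 makes operative has no row describing a first hip, knee or shoulder replacement and includes two procedures that are not joint replacement. This is a rule that gives the wrong cohort if followed as written, as distinct from a detail left unstated. For VTE, the documents support only a request to check coverage.

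The numbers wrongly kept or dropped, and any effect on the hazard ratios, cannot be computed from the documents. They are probably small, given the AF and CAD requirements.

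The conclusion assumes that the printed block is complete, that codes are applied as printed, and that K083-2 belongs to the block. Nothing in the text suggests lost or blacked-out rows, but the source file should settle all three.

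**What to change.** Before cohort extraction:

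1. Compare the printed joint-replacement block with the source code file. Confirm that no rows were lost, which block K083-2 belongs to, and whether codes are matched exactly or by prefix.
2. Add the procedure codes for first (primary) joint replacement, and delete K083 and K083-2.
3. Check whether I26, I26.0, I26.9 and I80.2 cover every deep-vein thrombosis diagnosis that exclusion 3 intends, and extend the list if they do not.
4. Record the final lists in Annex 2, so that the exclusion 3 row of Table 1 counts what its label says.

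The cost is a code-list edit and a slightly smaller cohort. No change to the statistical model is needed.

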**MEDICATION CODE:**

Medication	Receipt Code	Description
Anti-platelet injection	620004669	Shiphos I.V.Injection 10mg 0.5%2mL [C01D0]
	620008786	Agilease I.V.Injection 10mg 0.5%2mL [C01D0]
	620008891	Tohmol I.V.Injection 10mg 0.5%2mL [C01D0]
	620008931	Persantin I.V.Injection 10mg 0.5%2mL [C01D0]
	620330301	Dipyridamole I.V.Injection 10mg (ISEI) 0.5%2mL [C01D0]
	620330502	Dipyridamole I.V.Injection 10mg (NICHIIKO) 0.5%2mL [C01D0]
	642170001	Agilease Injection 0.5%2mL [C01D0]
	642170008	Tohmol Injection 0.5%2mL [C01D0]
	642170009	Persantin Injection 0.5%2mL [C01D0]
Anti-platelet Drug	codes presented in the following excel file:   1160-0308 Anti-platelet drug.xlsx	

**ANNEX 3. CODE USED FOR OUTCOMES**

Indication	ICD-10 code	Description
------------	-------------	-------------

# BOEHRINGER INGELHEIM Group of Companies

## Statistical and Epidemiological Analysis Plan (SEAP) for Non-Interventional Studies (NIS)

c38948754-01

Page 22 of 32

Proprietary confidential information © 2022 Boehringer Ingelheim International GmbH or one or more of its affiliated companies

Blood transfusion	K92.0	Haematemesis
	D50	Iron deficiency anaemia
	D50.0	Iron deficiency anaemia secondary to blood loss (chronic)
	D50.1	Sideropenic dysphagia
	D50.8	Other iron deficiency anaemias
	D50.9	Iron deficiency anaemia, unspecified
	D62	Acute posthaemorrhagic anaemia
	D64.9	Anaemia, unspecified
	H35.6	Retinal haemorrhage
	I31.2	Haemopericardium, not elsewhere classified
	I60	Subarachnoid haemorrhage
	I60.0	Subarachnoid haemorrhage from carotid siphon and bifurcation
	I60.1	Subarachnoid haemorrhage from middle cerebral artery
	I60.2	Subarachnoid haemorrhage from anterior communicating artery
	I60.3	Subarachnoid haemorrhage from posterior communicating artery
	I60.4	Subarachnoid haemorrhage from basilar artery
	I60.5	Subarachnoid haemorrhage from vertebral artery
	I60.6	Subarachnoid haemorrhage from other intracranial arteries
	I60.7	Subarachnoid haemorrhage from intracranial artery, unspecified
	I60.8	Other subarachnoid haemorrhage
	I60.9	Subarachnoid haemorrhage, unspecified
Bleeding	I61	Intracerebral haemorrhage
	I61.0	Intracerebral haemorrhage in hemisphere, subcortical
	I61.1	Intracerebral haemorrhage in hemisphere, cortical
	I61.2	Intracerebral haemorrhage in hemisphere, unspecified
	I61.3	Intracerebral haemorrhage in brain stem
	I61.4	Intracerebral haemorrhage in cerebellum
	I61.5	Intracerebral haemorrhage, intraventricular
	I61.6	Intracerebral haemorrhage, multiple localized
	I61.8	Other intracerebral haemorrhage
	I61.9	Intracerebral haemorrhage, unspecified
	K92.2	Gastrointestinal haemorrhage, unspecified
	M25.0	Haemarthrosis
	M25.00	Haemarthrosis, multiple sites
	M25.01	Haemarthrosis, shoulder region
	M25.02	Haemarthrosis, upper arm
	M25.03	Haemarthrosis, forearm
	M25.04	Haemarthrosis, hand
	M25.05	Haemarthrosis, pelvic region and thigh
	M25.06	Haemarthrosis, lower leg

Proprietary confidential information © 2022 Boehringer Ingelheim International GmbH or one or more of its affiliated companies

	M25.07	Haemarthrosis, ankle and foot
	M25.08	Haemarthrosis, other
	M25.09	Haemarthrosis, site unspecified
	N92.0	Excessive and frequent menstruation with regular cycle
	R04	Haemorrhage from respiratory passages
	R04.0	Epistaxis
	R04.1	Haemorrhage from throat
	R04.2	Haemoptysis
	R04.8	Haemorrhage from other sites in respiratory passages
	R04.9	Haemorrhage from respiratory passages, unspecified
	R31	Unspecified haematuria
	R58	Haemorrhage, not elsewhere classified
Stroke/SE/MI/ICH/Maj or GI bleeding/Death	codes presented in the following excel file:   1160-0308 stroke_SE_MI_GI_ICH_.xlsx	

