##### **Primary outcome:**

- Fatal or non-fatal major bleeding (defined as any blood transfusion and/or any hospitalization with associated bleeding) in all three patient groups

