### **8.2 OUTCOMES**

#### **8.2.1 Primary outcomes**

Operational definition of fatal or non-fatal major bleeding is the first new confirmed diagnosis of

- blood transfusion (inpatient or outpatient)  
OR
- bleeding of inpatient (non-DPC hospital)  
OR
- bleeding of inpatient (DPC hospital) with “disease name behind this hospitalization” (“dpcdiseasesegment”=21)

during the follow up period. The ICD-10 diagnosis codes of blood transfusion and bleeding are in [Annex 3](#).

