#### **8.2.2 Secondary outcomes**

Operational definition of composite outcome of stroke/SE/MI/all-cause mortality (inpatient)/major bleeding/major GI bleeding (hospitalization due to GI bleeding)/ICH is the first new confirmed diagnosis of

- Stroke/SE/MI/ Major bleeding (defined as primary outcome)/ICH  
OR
- Major GI bleeding (hospitalization due to GI bleeding)  
OR
- All-cause mortality (inpatient)

during the follow up period. The ICD-10 diagnosis codes of stroke, SE, MI, major bleeding, ICH, major GI bleeding and death are in [Annex 3](#).

Major GI bleeding (hospitalization due to GI bleeding) is the first new confirmed diagnosis of major GI bleeding in inpatient claims from non-DPC hospital or inpatient claims with “disease name behind this hospitalization” (“dpcdiseasesegment”=21) from DPC hospital.

All-cause mortality (inpatient) is:

Proprietary confidential information © 2022 Boehringer Ingelheim International GmbH or one or more of its affiliated companies

- Death of discharge status
  - OR
- Died within 24 hours of admission in FF1 data (discharge summary data)
  - OR
- Confirmed diagnosis of death in inpatient claims.

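### The closed code list behind the primary outcome leaves out site-specific GI and some intracranial bleeds that the protocol's definition of major bleeding includes

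*SAP*

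**What the plan says.** Protocol 9.3.2.1 defines the primary outcome as fatal or non-fatal major bleeding. It is met by any transfusion or by "any hospitalization with associated bleeding". There is no restriction by body site.

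SAP 8.2.1 turns this into diagnoses: "The ICD-10 diagnosis codes of blood transfusion and bleeding are in" Annex 3. In non-DPC hospitals, an inpatient diagnosis from the bleeding list is enough. In DPC hospitals it must also be flagged as the disease behind the admission. The transfusion limb is likewise a diagnosis-code limb, accepts inpatient or outpatient records and carries no such flag.

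The Annex 3 list as printed contains:
- haematemesis (K92.0)
- seven anaemia lines (D50 and subcodes, D62, D64.9)
- retinal haemorrhage and haemopericardium
- I60 and I61 with all their subcodes
- K92.2, "Gastrointestinal haemorrhage, unspecified"
- haemarthrosis, excessive menstruation and respiratory-tract bleeding
- unspecified haematuria (R31) and haemorrhage not classified elsewhere (R58)

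Stroke, SE, MI, ICH, major GI bleeding and death have a separate row, with "codes presented in the following excel file". SAP 8.2.2 uses that row for the composite: "Major GI bleeding (hospitalization due to GI bleeding) is the first new confirmed diagnosis of major GI bleeding in inpatient claims from non-DPC hospital", or the flagged equivalent in DPC hospitals. The composite joins major bleeding (as in the primary outcome), ICH and major GI bleeding by OR.

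**The concern.** The protocol's definition is open and the SAP's list is closed. Where the list has no entry for a type of bleed, an admission for that bleed counts under the protocol but not under the SAP.

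The gap falls on sites that matter for anticoagulated patients, many of whom also take antiplatelets. The plan itself treats upper-GI risk as important: peptic ulcer disease, proton pump inhibitors and gastric secretion inhibitors are all baseline covariates. Subarachnoid and intracerebral haemorrhage are listed in full, whereas GI bleeding has one symptom code and one unspecified code.

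The structure of SAP 8.2.2 points the same way. Under the protocol's wording, every admission for GI bleeding or ICH is already major bleeding, so adding those components to the composite would be redundant. If the separate lists add any such admission, the primary and secondary analyses use different meanings of major bleeding. The primary hazard ratio would then describe a subset of bleeds selected partly by site, and it could differ from the hazard ratio for the outcome the protocol names.

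**Working it through.** **1. Enumeration.** No stated figure is at issue, so the check is a line-by-line reading of Annex 3. Leaving aside K92.0, the printed list has 51 lines: I60–I61 21, haemarthrosis 11, anaemia 7, respiratory 6, and one each for K92.2, R31, R58, retinal, pericardial and menstrual bleeding (21 + 11 + 7 + 6 + 6 = 51). A search by code and by description found no line for ulcer with haemorrhage, melaena, rectal or other lower-GI bleeding, or subdural or other non-traumatic intracranial haemorrhage. I60 and I61 appear as parent categories, but K92 does not, and the line after I61.9 is K92.2. The text extraction has blurred the border between the Blood transfusion and Bleeding labels, but these entries are absent wherever it lies.

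**2. Logic of the composite.** Let P be the admissions caught by the primary list, and G those caught by the GI and ICH lists. Under the protocol, G lies wholly within major bleeding. Under the SAP, an admission in G but not in P is a composite event and not a primary event. Whether such admissions exist depends on a spreadsheet that is not visible here. If there are none, taking the union changes nothing.

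**3. Effect on the HR.** Let *s* be the share of warfarin-arm major bleeds that are unlisted. The overall hazard ratio is a weighted mean, so

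HR(listed) = (0.66 − *s* × HR(unlisted)) / (1 − *s*).

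The 0.66 is the planning value for dabigatran in Protocol 9.5. Both *s* and HR(unlisted) are assumptions, because the documents give neither.

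| HR(unlisted) | *s* = 20% | *s* = 30% | *s* = 40% |
|---|---|---|---|
| 1.0 | 0.575 | 0.514 | 0.433 |
| 0.8 | 0.625 | 0.600 | 0.567 |
| 0.66 | 0.660 | 0.660 | 0.660 |
| 0.5 | 0.700 | 0.729 | 0.767 |

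For example, (0.66 − 0.2 × 1.0)/0.8 = 0.575 and (0.66 − 0.4 × 0.5)/0.6 = 0.767. The listed-code HR moves below or above 0.66 according to whether the unlisted HR is above or below it.

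**4. Effect on power.** First, the plan's own figure. With two-sided alpha 0.05 (assumed, since it is not stated), 80% power and 1:1 allocation, Schoenfeld's formula gives 4 × (1.960 + 0.842)² / (ln 0.66)² ≈ 182 events. Then 182/0.03 = 6,067, against the stated 6,050. The stated size therefore reproduces closely.

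At the stated minimum of 6,050 patients (181.5 events), losing 20% or 40% of events lowers power from 80% to 71% or 58%. Protocol 9.5, however, expects about 4,000 dabigatran and 17,000 warfarin patients. At 3 events per 100 patient-years and one year of exposure that is 21,000 × 0.03 = 630 events, with allocation factor (4/21) × (17/21) = 0.154. Power is Φ(√(events × 0.154) × |ln 0.66| − 1.96):

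| Dabigatran vs warfarin | 20% of events missed | 40% of events missed |
|---|---|---|
| Full expected cohort | 504 events, 96% | 378 events, 89% |
| After a further 20% sample loss (Protocol 9.5) | 403 events, 91% | 302 events, 81% |

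These figures ignore the extra variance from weighting.

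**The case against.** Four points can be made against this, and each has some force.

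- **A reader might infer that these admissions can never be primary events.** The documents do not support that. A GI bleed coded K92.2 counts. So can a bleeding-ulcer admission that also carries a new anaemia code (D50.0, D62, D64.9). If those codes belong to the transfusion limb, no DPC flag is needed; if they belong to the bleeding limb, the flag applies in DPC hospitals. The loss is confined to admissions with none of the listed codes. Capture through an accompanying anaemia code is, however, incidental to the bleed and does not make the two definitions agree.

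- **A reader might infer that the primary HR is biased in the NOAC's favour.** That follows only if the relative effect on the unlisted bleeds is less favourable than overall. The unlisted group mixes GI with subdural and other intracranial bleeding, and the documents give no hazard ratio for either. The table above shows movement both ways.

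- **The GI and ICH results will be visible anyway.** Both are components of the composite, the components are further outcomes, and SAP 11.1 fits Cox models to them. This helps interpretation but leaves the primary outcome narrower than its definition.

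- **The table is damaged and the spreadsheet is unseen.** This is true, and neither is a fault of the plan. The missing entries are absent under either reading of the table, and SAP 8.2.1 does not bring the GI and ICH row into the primary definition. The documents also do not reproduce the ICD-10 classification, so the point assumes that some admissions are coded to a specific site.

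Nor is the list mainly unspecified codes plus I60–I61: those make up 26 of 51 lines, and line counts say nothing about event counts.

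**Conclusion.** The concern holds as a mismatch between protocol and SAP. Followed as written, the SAP yields a primary outcome narrower than the protocol's for GI bleeding and for intracranial bleeding outside I60–I61. It also lets major bleeding carry two meanings across the primary and secondary analyses.

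The size cannot be settled from the documents. Under the assumed 20 to 40% unlisted, the dabigatran HR on listed codes could lie anywhere from about 0.43 to 0.77 around a true 0.66, as the unlisted HR ranges from 1.0 to 0.5. With no difference by site there is no bias of this kind. The same list serves the rivaroxaban comparison.

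A reader might also take the 71% and 58% power figures as this study's power. They apply to the minimum size only. At the expected size, power stays at 81% or above in the cases shown, and the anaemia codes may add events that offset part of the loss. The validity and consistency of the outcome are the main issue; power is secondary.

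**What to change.** In SAP 8.2.1 and Annex 3:

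1. Define the bleeding limb as the union of the printed Bleeding list with the Major GI bleeding and ICH lists already held in the Annex 3 spreadsheet, under the same inpatient rule.
2. Confirm that the union covers site-specific GI haemorrhage (ulcer with haemorrhage, melaena, lower GI) and subdural and other non-traumatic intracranial haemorrhage.
3. Report the printed list as a sensitivity definition, so that the effect of the change on event counts and on the HR can be seen.

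If the narrower outcome is in fact intended, the protocol definition should say so, and the two documents should be reconciled on that basis.

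The cost is an edit to SAP 8.2.1 and Annex 3 and one re-run of the outcome query, with no new data. The downside is a slightly wider outcome and an event rate that may differ somewhat from the 3 to 4.5 per 100 patient-years assumed in Protocol 9.5.
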